Kisspeptin Physiology in Patients with Hyperprolactinemia

NCT02956447

Study Protocol and Statistical Analysis Plan

6/14/23

Kisspeptin Physiology in Patients with Hyperprolactinemia

BROAD GOALS

The overall goals of this protocol are to stimulate gonadotropin secretion and folliculogenesis using exogenous kisspeptin administration.

SPECIFIC AIMS

Aim 1: To stimulate gonadotropin secretion using exogenous kisspeptin.

Hypothesis: The inhibitory effect of hyperprolactinemia on GnRH secretion is mediated through kisspeptin. Therefore, kisspeptin administration to hyperprolactinemic women intolerant to conventional therapies will result in an increase in GnRH-induced gonadotropin release.

Aim 2: To stimulate folliculogenesis using exogenous kisspeptin.

Hypothesis: The suppression of folliculogenesis that occurs in hyperprolactinemia can be overcome by kisspeptin administration. Therefore, kisspeptin administration to hyperprolactinemic women intolerant to conventional therapies will result in mature follicle development.

SUBJECT SELECTION

This study will consist of two cohorts, one for each specific aim.

Inclusion/Exclusion Criteria

Inclusion:

- Female, Ages 18-45,
- Confirmed diagnosis by elevated levels of prolactin measured via blood test
- Physical Examination:
 - normal blood pressure, (systolic BP < 140 mm Hg, diastolic < 90 mm Hg).
- Laboratory Studies:
 - white blood cell, platelet counts, and TSH between 90% of the lower limit and 110% of the upper limit of the reference range,
 - hemoglobin no less than 0.5 gm/dL below the lower limit of the reference range for normal women,
 - BUN, creatinine, AST, ALT not elevated,
 - negative serum hCG pregnancy test at the time of screening (additional urine pregnancy test will be conducted prior to drug administration).
- Willing to complete a dopamine agonist washout period 6 ± 2 weeks prior to each of the frequent blood sampling visits (Cohort 1) or 6 ± 2 weeks prior to completing relevant screening labs until the end of the study (Cohort 2). The washout period will last at least 4 weeks.
- Not using oral contraceptives or willing to complete an oral contraceptive washout period 8 weeks prior to each of the frequent blood sampling visits (Cohort 1) or 8 weeks prior to completing relevant screening labs until the end of the study (Cohort 2).

Exclusion:

- Patients with a macroprolactinoma confirmed on MRI Imaging

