The screening history may be obtained by phone. Documentation of a physical examination performed by a non-study physician within the previous 12 months may be used in lieu of an in-person physical examination; in this case, a physical examination will also be performed by a study physician at Visit 1. To obtain physical examination results performed off-site, subjects will be given an MGH "authorization for disclosure of medical information from another facility" form. If a physical examination is performed solely for the purposes of this study, study funds will pay for the cost of the physical examination. Remote screening laboratory studies will be performed at MGH on a blood sample shipped by the subject or at a local laboratory site (e.g. LabCorp,

Quest, etc.); study funds will pay for all phlebotomy and shipping costs. Laboratory studies already performed within the previous 6 months will be in lieu of repeating screening studies unless abnormal.

Cohort 1 Protocol: Gonadotropin secretion (N=10)

Subjects will complete four outpatient visits. Procedures for each visit are described below:

Screening Visit: Described above

If eligibility criteria are all met, a member of the study team will call the subject and schedule them for two visits at the Clinical Research Center.

As mentioned above, we will ask subjects being treated with dopamine agonists to complete a washout period prior to the frequent blood sampling visit(s). The washout period will last at least 4 weeks.

Visit 1

- Admission to the Clinical Research Center (CRC)
- q10 minute blood sampling (3 mL q 10 min) x 12 hours without intervention to assess endogenous LH pulsatility. All samples will be assayed for LH. Progesterone (P4) will be measured on the first sample. FSH, prolactin, and estradiol (E2) will be assayed from pools of the frequent sampling studies.^{3,4}

Visit 2 (within 22 days of Visit 1)

- Admission to the Clinical Research Center (CRC)
- q10 minute sampling (3 mL q 10 min) x 12 hours
- Administration of 10 boluses of kisspeptin 0.313 µg/kg IV every hour beginning at hour 1 of the study. All samples will be assayed for LH. Progesterone (P4) will be measured on the first sample. FSH, prolactin, and estradiol (E2) will be assayed from pools of the frequent sampling studies.^{3,4}
- Administration of one bolus of GnRH 0.075 ug/kg IV at hour 11 of the study.

Visit 3: Final follow-up study visit

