The total volume of blood drawn during screening is 13-18mL. Subjects will then undergo daily monitoring blood draws over 7 days. Total volume of blood drawn during Visits 1-7 will not exceed 30mL each day. The total volume of blood drawn during Visit 8 will not exceed 20mL. The total volume of blood drawn over the course of the protocol is within the PHRC guidelines and will not exceed 550 mL.

If a study subject wants to participate in both Cohort 1 & Cohort 2, there will be a minimum of 8 weeks between study participation in Cohort 1 and participation in Cohort 2, to conform with PHRC guidelines.

Justification of doses:

Kisspeptin IV: The dose of kisspeptin 112-121 0.313 µg/kg (0.24 nmol/kg) IV x1 is the same dose used in the PI's studies in healthy men and women and is the dose predominantly used in the PI's studies of men with IHH. This dose was chosen based on the first reported use of kisspeptin in humans, which showed that doses smaller than this dose (using a molar equivalent) elicited a smaller response (rise in LH), whereas larger doses did not elicit a larger response.⁵ In other words, a dose of 0.24 nmol/kg was the smallest dose to elicit a maximal response. A more recent report of dose-response studies with kisspeptin made similar findings.⁶ The LH amplitudes of kisspeptin-induced-GnRH- induced LH pulses are comparable to the LH amplitudes observed endogenously during the follicular and luteal phases of the female menstrual cycle have LH amplitudes comparable to (follicular phase: kisspeptin induced LH amp 1.1 ± 1.0 vs. endogenous LH amp 1.2 ± 0.5 mIU/mL; mid-luteal phase: kisspeptin induced LH amp 4.0 ± 2.8 vs. endogenous LH amp 3.0 ± 1.5 mIU/mL)⁷ Moreover, in men, the range of LH amplitudes observed for kisspeptin-induced-GnRH-induced pulses overlaps the range of amplitudes that occurs endogenously (1.6 –10.9 and 0.5–7.8 mIU/ml, respectively).⁸ Thus, kisspeptin 0.24 nmol/kg (0.31 µg/kg) is a physiologic dose in healthy adults.

Kisspeptin SC: The dose range of kisspeptin 112-121 is 0.313 µg/kg (0.24 nmol/kg) – 13.19 µg/kg (10.1 nmol/kg). A range of doses is provided to account for a differential response of SC administration as compared to IV administration, as confirmed by the PI's other work.

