Termination criteria will include: 1) blood pressure > 180 mmHg systolic or > 105 mmHg diastolic at any point during the protocol; 2) development or suspicion of an allergic or serious adverse reaction; 3) positive pregnancy test; 4) temperature $\geq 101.5^{\circ}\text{F}$ at any point in the study. Any subject who develops high blood pressure or an allergic reaction will receive follow-up inpatient medical care until the issue is resolved, with subsequent outpatient and/or phone follow-up as needed.

BIOSTATISTICAL ANALYSIS

Assays

Given the long-term ongoing nature of this study, the assay methodologies employed to characterize the biochemical profile (both reproductive and metabolic) will be based on standard accepted methods as established by the Reproductive Endocrine Reference Laboratory. As such these methods may include immunoassays, measurement using standard laboratory platforms, radioimmunoassays, and mass spectroscopy. We anticipate that these methods will continue to evolve as the diagnostics field changes.

Cohort 1 (Specific Aim 1)

Population Size

Each patient will serve as her own control. The primary outcome will be the number of LH pulses on the first biochemical assessment (no kisspeptin) compared to the second assessment (+kisspeptin). Many studies in the literature have reported a decreased LH pulse frequency in hyperprolactinemia with one study (using q 10 minute sampling) documenting approximately 2.25 pulses / 12 h in hyperprolactinemic individuals.¹² During the second admission, by administering 10 boluses of kisspeptin, 10 LH pulses should be observed. For the purposes of these calculations however, 8 pulses will be conservatively estimated because some of those pulses will coincide with/conceal endogenous pulses. For a difference of 8 and an SD of 6.8, 10 subjects will need to be studied before and after kisspeptin to achieve 90% power at alpha = 0.05.

Data Analysis and Interpretation

LH pulses will be identified using a modified version of the Santen and Bardin method of pulse detection which has been validated *in vivo*.^{3,4} The primary outcome will be change in the frequency of LH pulses in response to kisspeptin administration. The hypothesis will be accepted if the change in LH frequency on kisspeptin is higher during intermittent kisspeptin administration (second assessment) than in the absence of kisspeptin administration. Mean LH level and LH pulse amplitude will also be calculated and used in secondary analyses.

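### Cohort 1's acceptance rule takes in a claim of mediation through kisspeptin that a rise in LH pulse frequency does not by itself establish

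*Combined protocol and SAP*

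**What the plan says.** Under Specific Aims, Aim 1 has a single labelled hypothesis in two sentences. The first is a mechanism: "The inhibitory effect of hyperprolactinemia on GnRH secretion is mediated through kisspeptin". The second follows from it as a consequence: giving kisspeptin to these women "will result in an increase in GnRH-induced gonadotropin release".

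Under Biostatistical Analysis, Cohort 1, Data Analysis and Interpretation, the primary outcome is the change in LH pulse frequency, and the rule is: "The hypothesis will be accepted if the change in LH frequency on kisspeptin is higher during intermittent kisspeptin administration (second assessment"), compared with no kisspeptin. The rule does not say which part of the hypothesis is accepted, and it names no test or significance level.

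The comparison is within subject: "Each patient will serve as her own control". Visit 1 is 12 hours of sampling without intervention. Visit 2 is 12 hours with "Administration of 10 boluses of kisspeptin 0.313 µg/kg IV every hour beginning at hour 1 of the study", then one GnRH bolus at hour 11. The assays listed are LH, FSH, prolactin, estradiol and progesterone.

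On the IV dose, the Justification of doses section says it "is the same dose used in the PI's studies in healthy men and women", that "a dose of 0.24 nmol/kg was the smallest dose to elicit a maximal response", and that it "is a physiologic dose in healthy adults".

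**The concern.** The rule treats confirmation of a prediction as acceptance of the premise from which it was drawn. That is safe only if the prediction would be unlikely to come true were the premise false. Here the protocol's own dose section describes LH pulses after the same dose in healthy men and women, for whom no prolactin-related kisspeptin deficit is claimed. Pulses after boluses are thus what one would expect from any GnRH neuron and pituitary still able to respond, by whatever route prolactin slows them.

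At stake is the conclusion the trial may draw. This sentence is the plan's only stated interpretation of Aim 1. Followed literally, it turns evidence that the axis responds to exogenous kisspeptin into acceptance of a causal pathway. It would do so even if prolactin reduced the drive to responsive GnRH neurons without involving kisspeptin.

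**Working it through.** **1. What the dose section documents.** Comparison of LH pulse amplitudes, from Justification of doses:

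| Group | Kisspeptin-induced (mIU/mL) | Endogenous (mIU/mL) |
|---|---|---|
| Women, follicular phase | 1.1 ± 1.0 | 1.2 ± 0.5 |
| Women, mid-luteal phase | 4.0 ± 2.8 | 3.0 ± 1.5 |
| Men (range) | 1.6–10.9 | 0.5–7.8 |

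These are amplitudes, for a dose described as given once. They are not pulse-frequency data for ten hourly boluses, and none come from hyperprolactinemic women. The expected rise in frequency comes instead from the Population Size section, which anticipates 10 pulses from 10 boluses (8 as a conservative figure) against about 2.25 per 12 h at baseline.

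**2. Predictions of the competing explanations.**

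| Explanation of the low pulse frequency | Expected pulse frequency on kisspeptin |
|---|---|
| Prolactin acts through kisspeptin; downstream axis responsive | Rises |
| Prolactin slows GnRH by another route; GnRH neuron and pituitary still responsive | Rises |
| Complete block downstream of kisspeptin | Does not rise |

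The rule separates the third row from the first two. It does not separate the first from the second.

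**3. Whether anything else in Cohort 1 separates those two.**
- There is no normoprolactinemic comparison group and no assay of endogenous kisspeptin.
- There is no designed contrast in prolactin: the eligibility criteria place the dopamine agonist washout before each sampling visit.
- The hour-11 GnRH bolus checks pituitary responsiveness. It does not show which pathway prolactin uses.
- Pooled prolactin at both visits can show whether prolactin fell on kisspeptin. The dose section expects no significant change. This addresses the possibility that kisspeptin works by lowering prolactin, not mediation.

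**4. The plan's own figure.** Inputs from Population Size: difference 8, SD 6.8, N = 10, 90% power, alpha 0.05 (sidedness not stated). Taking 6.8 as the SD of within-subject differences, the noncentrality is 8 / (6.8/√10) = 8 / 2.150 = 3.72. A two-sided paired t-test on 9 degrees of freedom then has 91.0% power, and N = 10 is the smallest N reaching 90%. The figure reproduces.

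**5. How often the rule is met if the boluses work.** The rule is read as mean pulse frequency being higher at Visit 2. By normal approximation, P(met) = Φ(d / (SD/√10)). The column for a significant rise uses the two-sided paired t-test at 0.05.

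| Difference d | SD | Literal rule met | Significant rise |
|---|---|---|---|
| 8 (as planned) | 6.8 | >99% | 91% |
| 10 − 2.25 = 7.75 | 6.8 | >99% | 89% |
| 8 − 2.25 = 5.75 | 6.8 | >99% | 66% |
| 0.5 × 10 − 2.25 = 2.75 (assumed) | 6.8 | 90% | 21% |
| 2.75 (assumed) | 4 (assumed) | 98% | 49% |
| 2.75 (assumed) | 2 (assumed) | about 100% | 97% |

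The last three rows assume that only half the boluses produce a pulse and that no endogenous pulse is added.

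These are probabilities given that the axis responds. No input depends on whether prolactin acts through kisspeptin, so they apply equally to the first two rows of the table in step 2. They do not measure the weight of evidence between mechanisms. That would need the probability of a response under each one, which the documents do not give.

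**The case against.** The best defence is that the word hypothesis in the rule may mean only the operational prediction. The broad goal and the title of Aim 1 are about stimulating gonadotropin secretion, and the rule directly follows the definition of the primary outcome, which matches that prediction. This reading is possible, but it is not what the text says: there is one labelled hypothesis for Aim 1, it begins with mediation, and the rule does not exclude that part.

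A second defence is that the consequence is small. No endpoint, test or procedure changes, and no decision is tied to acceptance. That is true, and it is why the remedy is confined to wording. It does not make the present wording correct.

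A reader might also infer something stronger: that a positive result cannot support mediation at all, or that it is a foregone conclusion carrying almost no information. The documents do not support that. The dose evidence concerns amplitude after a single dose in healthy adults. The figure of one pulse per bolus is a planning assumption, and a response in hyperprolactinemic women is not guaranteed. The prediction could fail, and failure would count against it. Success is consistent with mediation and argues against a complete block downstream of kisspeptin. The GnRH bolus and the prolactin assays narrow the alternatives further, by addressing pituitary unresponsiveness and a fall in prolactin.

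**Conclusion.** The concern holds as a limit on what may be concluded. A higher LH pulse frequency at Visit 2 would support the statement that intermittent kisspeptin raises pulse frequency in hyperprolactinemic women. It would not by itself establish that prolactin's effect on GnRH is mediated through kisspeptin, because the same rise is expected from any other mechanism that leaves the GnRH neuron and pituitary responsive.

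The conclusion rests on reading the hypothesis as the whole Aim 1 statement and on the protocol's own expectation about the boluses. If that expectation is right, acceptance is very likely under both explanations; if it is wrong, the rule may well not be met. How strongly a positive result would favour one mechanism over the other cannot be calculated from the documents. The sample size, primary endpoint and test of the prediction are unaffected. The change should be made, because the acceptance sentence determines what the trial may claim.

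**What to change.** In Data Analysis and Interpretation for Cohort 1, replace the acceptance sentence with: *If LH pulse frequency is higher with kisspeptin, we will conclude that intermittent kisspeptin increases GnRH-induced LH pulse frequency in hyperprolactinemic women; this does not by itself establish that the effect of hyperprolactinemia is mediated through kisspeptin.*

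Under Specific Aims, Aim 1, present the mediation sentence as the rationale for the prediction, and leave the prediction as the hypothesis to be tested.

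The cost is two changes of wording and a narrower claim. No data, visits, endpoint or sample size change.
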